5.3.3.1 Software Implementation and Validation

The reference based imputation methodology will be implemented by an internally developed R package “rbmi” (“reference-based multiple imputation”). The package will comply with the ICH guidance document “ICH E 9: Statistical principles for clinical trials” which states that: “The computer software used for data management and statistical analysis should be reliable, and documentation of appropriate software testing procedures should be available.”

The testing strategy for the package consists of defining and documenting the expected input and output of each function and implementing unit tests to prove that the package performs as expected. All implemented methods will be recorded and referenced against the literature with unit tests and simulations put in place to show that known values can be recovered as well as showing consistency with similar software from other languages (most notably the “5-Macros” implemented by the Drug Information Association Scientific Working Group on Estimands and Missing Data in SAS).

The package, including all documentation and testing materials, is available on GitHub.com (<https://github.com/insightengineering/rbmi>) and on CRAN repository (<https://cran.r-project.org/package=rbmi>) to allow for unrestricted access and enable public scrutiny of the code and methods. Description of the rbmi package is also available on a published manuscript (Gower-Page et al. 2022).

The rbmi R package was validated by the in-house tool, Autovalidate R, which performs general R package quality checks and performs testing for expected behaviors.

5.3.4 Sensitivity Analyses for Primary Endpoint

Impact of COVID-19 pandemic

The following sensitivity analyses will be performed to evaluate the impact of the COVID-19 pandemic:

- Vary threshold on number of missed dose-months due to the pandemic in the definition of “substantial reduction in drug exposure” ICE. The “substantial reduction in drug exposure” ICE is defined with a threshold ≥ 4 dose-months (not necessarily consecutive). A sensitivity analysis will be performed using different thresholds: 1, 2, 3, 5 and 6 dose-months. All other aspects of the primary estimator will remain the same.
- Exclude participants based on site closure information and apply a treatment policy strategy to all other COVID-19 related ICEs. In this analysis, all participants enrolled before a site closure due to the pandemic will be removed from the analysis set. In alignment with the primary estimand, only a site closure of 16 weeks or more during the double-blind treatment period and without any access to study drug (no home nursing) will be considered. In accordance with the FDA’s guidance for Industry “Statistical Consideration for Clinical Trial During the COVID-19 Public Health Emergency (June 2020)”, participants excluded from this analysis can be identified using baseline data only: randomization date and site number. The site closure information is an administrative site level information, independent of the conduct of the trial, collected using the eCRF for the purpose of this study and analysis. The substantial reduction in drug exposure due to the COVID-19 pandemic (defined as ≥ 4 missed dose-months) will not be considered as an ICE. All other aspects of the primary estimator will remain the same.
- Remote scale administration. Remote scale administration was authorized in exceptional cases at Weeks 104 and 116 visits due to COVID-19 related restrictions. In this analysis, all CDR-SB assessments performed remotely will be excluded from the analysis and treated as missing data. All other aspects of the primary estimator will remain the same.
- A subgroup analysis based on the date of randomization. This will allow estimating the treatment effect for subgroups of participants randomized at least 12 months before the onset of the global COVID pandemic (11 March 2020 according to the World Health Organization ([WHO](#)) opening remarks), in ≥ 5 to 12 months prior to the onset of the global COVID pandemic and within less than 5 months from the onset of the global COVID pandemic (see Section 5.3.5.1 for an exact definition of each subgroup).

Impact of missing data handling methods

The following sensitivity analyses will be performed to evaluate the impact of missing data handling method:

- Tipping point analysis

This analysis stress tests the CIR assumption by imputing worse outcomes after SDCR ICEs in the active drug arm than predicted by the CIR assumption. This will be implemented via a marginal δ -approach as described in the 'rbmi: advanced functionality' vignette of the rbmi's package and in Cro et al, 2020. Specifically, the imputation step will be performed as for the primary estimator and, after imputation is completed, a constant δ will be added to the imputed week 116 outcomes occurring after SDCR ICEs in the active drug arm. The subsequent analysis step of these δ -adjusted imputed datasets is as for the primary estimator.

To determine the tipping point, the constant δ will be increased in small steps starting from a value of 0 (corresponding to the primary estimator). The tipping point will then be defined as the value of δ at which the p-value for the treatment effect estimator first becomes greater than 5%.

Impact of potential outliers or extreme observations

In order to assess the impact of a potentially small number of "extreme observations" or "outlier points" (e.g., rapid progressors) on the treatment effect, the ANCOVA analysis model will be replaced by a robust linear regression. Robust regression will produce treatment effect estimates less contaminated by highly influential observations. Specifically, robust regression using M estimation will be used. Standard errors and confidence intervals will be based on jackknife as described previously.

5.3.5 Supplementary Analyses for Primary Endpoint

5.3.5.1 Subgroup Analyses for Primary Endpoint

The generalizability of the CDR-SB results when comparing the active drug arm to the placebo arm will be investigated by estimating the treatment effect in the following subgroups:

- Demographics:
 - Age, two age categories cut by the median
 - Sex
 - Geographic Region, as per IxRS
- Baseline disease severity:
 - CDR-GS = 0.5 vs CDR-GS > 0.5
 - Prodromal vs Mild (as per eCRF)

- APOE ε4 genotype
 - Carrier/Non Carrier
- Use of symptomatic AD medication at baseline Yes/No (derived from eCRF based on the search below)
 - Symptomatic AD medication is defined as any one of: donepezil, galantamine, memantine or rivastigmine
- Randomization date, three subgroups defined by the following dates:
 - *before* 11 March 2019
 - *in between* (and including) 11 March 2019 and 1 October 2019
 - *after* 1 October 2019

Summaries of the treatment effect for the change in CDR-SB from baseline to Week 116 by these subgroups will be provided in forest plots.

5.3.5.2 Other Supplementary Analyses for Primary Endpoint(s) Treatment effect estimates before Week 116

In this supplementary analysis, the same analysis strategy as described for the primary estimator will be used to estimate the effect of the active drug on disease progression defined as a change in CDR-SB at other time points, other than Week 116.

The treatment effect on the adjusted mean change in CDR-SB from baseline to Week 24, 52, 76 and 104 will be provided.

Treatment effect in relationship to a post-baseline timepoint

In this supplementary analysis, the same analysis strategy as described for the primary estimator will be used to estimate the percent relative difference between Week 52 and Week 116 as well as between Week 24 and Week 116, and between Week 76 and Week 116.

The relative difference between e.g., Week 52 and Week 116 (and similarly for the other considered post-baseline timepoints) will be defined as:

$$[(\text{Delta_wk_116} - \text{Delta_wk_52}) / (\text{Placebo_wk_116} - \text{Placebo_wk_52})] * 100$$

where Delta_wk_x is the estimated treatment effect at Week x, and Placebo_wk_x is the estimated change from baseline for the placebo arm at Week x. All those quantities will be obtained from the same model used for the primary estimand.

Treatment policy estimand

All ICEs will be handled with a treatment policy strategy regardless of whether being SDCR or NSDCR. All observed data will be included regardless of occurrence of any ICE. Missing values following all ICEs will be imputed with the method used in the primary estimator for missing data following an SDCR ICE, see Section 5.3.3. Missing values, not following an ICE, will be imputed under MAR (similarly to the primary estimands analysis, see “Missing data assumptions for the primary estimator” in Section 5.3.3). Note that the attributes of population, variables, treatment, and population level summary will remain the same as for the primary estimand.

Concomitant AD treatment estimand

In this supplementary analysis, the treatment effect will be evaluated in the hypothetical scenario that no post-baseline initiation or modification of the use of other approved AD medication has happened.

All attributes of this estimand except Treatment will be identical as for the primary estimator. The treatment attribute will be: “Prescribed study drug including uptitration to the target dose, irrespective of concomitant use of symptomatic treatment for AD at baseline, but assuming no initiation or change in symptomatic treatment after baseline”. In this supplementary analysis, all data following ICEs “Starting another treatment for AD” and “Changing the dose of a symptomatic treatment for AD” will be set to missing and imputed under a MAR assumption, in line with a hypothetical strategy. The analysis methods will be the same as described for the primary estimand.

MMRM

This analysis aims to provide a reference point analysis method described in early versions of the protocol (up to version 4) and to other external analyses where MMRM was considered the default and primary analysis. All available data will be used in the analysis. There will be no missing data imputation or consideration for any intercurrent events. The model will include the following covariates: treatment group, visit, and treatment-by-visit interaction, baseline CDR-SB score and baseline CDR-SB score-by-visit interaction, baseline ADAS-Cog 13 total score, baseline ADCS-ADL total score and the randomization stratification factors, namely: disease stage (from eCRF), geographic region (from the IxRS), the use of AD medication at baseline (from eCRF) and the APOE ε4 status (from the Vendor). An unstructured variance-covariance structure will be applied to model the within-subject errors across visits. In the case of non-convergence, compound symmetry will be used, together with a robust estimator of standard error (“sandwich” estimator).

Clinically evident decline: a progressor analysis

In this supplementary analysis, CDR-SB progression will be defined as a change from baseline in CDR-SB greater than or equal to a threshold x . The primary threshold of interest is $x=2.5$. The work justifying the threshold will be presented, as an oral presentation, at the Alzheimer's Association International Conference (AAIC), 31 July–4 Aug 2022; San Diego, CA and online (title of the oral presentation: *Selecting appropriate meaningful change thresholds for trials of early (prodromal-to-mild) AD: A caregiver-rated, anchor-based analysis based on the Tauriel Study*).

The CDR-SB progression endpoint will be analyzed using the same conditional mean imputed dataset as for the primary estimator of the primary estimand (Section 5.3.3).

The probability of CDR-SB progression by Week 116, in each treatment arm, will be estimated by the proportion of participants with a progression at any time during the double blinded period. The probability of progression by Week 116 will be obtained for different values of the progression threshold x . A plot of the probability of CDR-SB progression by Week 116 versus threshold values x will be generated.

In addition, a Cox proportional hazard model to estimate the treatment effect on time to first CDR-SB progression (based on the primary threshold of interest), may also be considered. In this case, the same baseline covariates as for the primary estimator of the primary estimand will be used (Section 5.3.3). An unadjusted model or a stratified analysis may be considered as well. Corresponding standard errors and confidence intervals will be calculated using the jackknife as previously described.

Impact of ARIA-E MRI finding on the primary outcome

In this supplementary analysis, the objective is to estimate the treatment effect, in the hypothetical scenario where ARIA-E would not have occurred. This analysis aims at removing the potential impact of ARIA-E on the primary endpoint.

All the attributes from the primary estimand will remain the same, but an ICE of 'ARIA-E occurrence' will be added. The 'ARIA-E occurrence' will be handled with hypothetical strategy. All data collected after the occurrence of an ARIA-E will be removed and treated as missing for this data analysis purpose. Post- ARIA-E data will then be imputed under the Missing at Random assumption unless ARIA-E is not the first ICE. In this case, the imputation will be determined by the strategy for the first ICE as described for the main estimator.

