shown to be ineffective in Studies WN25203 (SCarlet RoAD) and WN28745 (Marguerite RoAD).

- A 20% difference is the usual acceptability threshold to establish PK bioequivalence. The protocol includes 20 dose-months (80 weeks) at target dose after the up-titration period. Missing less than 4 dose-months results in an overall reduction in drug exposure of less than 20% of the total planned dose.

As a conservative approach, all withdrawals from study treatment due to an AE will be classified as SDCR for the purpose of the primary analysis. This includes withdrawal from study treatment due to suspected or confirmed COVID-19 infection AE, because the relationship of these events to the participant condition may be ambiguous.

All SDCR ICEs will be handled with a treatment policy strategy, while NSDCR ICEs will be handled with a hypothetical strategy. The frequencies of ICE will be summarized by treatment arm.

In this study, given the disease stage at baseline of the target population, death is expected to be a rare event and mostly not considered related to treatment or disease progression, and as such the corresponding ICE of death will be handled with a hypothetical strategy for the primary estimand. Of note, a supplementary estimand which defines all ICEs, including death, as SDCR (and thus using the same imputation strategy as for the other SDCR ICEs; see Section 5.3.3), is described in Section 5.3.5.

Table 3 Intercurrent Events Impacting Primary Analysis

| Intercurrent Event | SDCR/NSDCR | Estimand Approach |
|--|------------|-----------------------|
| Withdrawal from study treatment due to lack of efficacy | SDCR | Treatment Policy |
| Withdrawal from study treatment due to safety or tolerability reason (NOTE: This will include discontinuation due to AE, incl. suspected or confirmed COVID-19 AEs) | SDCR | Treatment Policy |
| Withdrawal from study treatment with no informative reason given | SDCR | Treatment Policy |
| Withdrawal from study treatment due to the COVID-19 pandemic | NSDCR | Hypothetical Strategy |
| Substantial reduction in drug exposure due to the COVID-19 pandemic (defined as ≥ 4 missed dose-months) | NSDCR | Hypothetical Strategy |
| Withdrawal from study treatment due to purely administrative reason | NSDCR | Hypothetical Strategy |
| Death | NSDCR | Hypothetical Strategy |
| Withdrawal from study treatment due to use or initiation of protocol prohibited medication | SDCR | Treatment Policy |

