For participants with multiple ICEs, the type of the first ICE will determine the strategy to be considered.

Missing data assumptions for the primary estimator

For intermittent missing data (i.e., for participants with non-missing Week 116 data but missing data at other visits), missing data not associated with an ICE (e.g., for participants who had completed Week 104 visit before protocol v4 was implemented), and for missing data after NSDCR ICEs (handled with a hypothetical strategy), the missing data are assumed to be similar to those from the other participants in the same treatment group with no such missing data. This is compatible with a missing-at-random (MAR) assumption.

All observed data after SDCR ICEs will be included in the analysis. If data after SDCR ICEs are missing, they will be assumed to be similar to those in the placebo group for both study arms. Specifically, data will be imputed based on the placebo arm using reference based imputation with a Copy Increments from Reference (CIR) assumption ([Carpenter et al, 2013](#) and [Cro et al, 2020](#)). This approach appears conservative yet plausible for the study drug. CIR assumes that changes in the primary endpoint after the ICE in a participant randomized to active drug can be represented by, i.e., imputed from, that of participants randomized to placebo. It therefore assumes no treatment effect after the ICE. In the placebo arm, this is compatible with a MAR assumption whereas in the active drug arm, the imputation is under a Missing Not At Random (MNAR) assumption.

Further details about the implementation of the missing data imputation are provided below. Sensitivity analyses for the missing data assumptions are discussed in Section 5.3.4.

Description of the primary estimator

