The imputation model includes the following covariates: treatment group, visit, and treatment-by-visit interaction, baseline CDR-SB score and baseline CDR-SB score-by-visit interaction, baseline ADAS-Cog 13 total score, baseline ADCS-ADL total score and the randomization stratification factors, namely: disease stage (from the eCRF), geographic region (from the IxRS), the use of AD medication at baseline (derived from the eCRF based on a search of medications; see below for more details) and the APOE ε4 status (from the Vendor). For geographic region, IxRS is preferred over the eCRF source, to keep the “starting” region for analysis, in case a participant moved to a different region during the study (the eCRF would otherwise reflect the “final” region). AD medication at baseline will be defined as any use of donepezil, galantamine, memantine or rivastigmine prior to randomization and with an

end date not before the randomization date. An unstructured variance-covariance structure will be applied to model the within-subject errors across visits. If the model fails to converge, then a heterogeneous Toeplitz covariance structure will be used instead and if this still fails, then a compound symmetry covariance structure will be used.

Imputations will be based on restricted maximum likelihood (REML) estimation of the regression and covariance parameters from the imputation model ([von Hippel and Bartlett 2021](#); [Wang and Robins 1998](#)).

2. Imputation step

The imputation model implies a marginal multivariate normal distribution of the longitudinal outcome values across all visits based on a participant's assigned treatment arm and covariate values. This marginal imputation distribution will be used for all participants in the placebo arm and all participants in the active drug arm without an SDCR ICE. For participants in the active drug arm with an SDCR ICE, the mean of the marginal imputation distribution for outcomes after the SDCR ICE will be modified as per the CIR assumption ([Carpenter et al. 2013](#)).

For each participant, the conditional imputation distribution of their missing outcome values is defined as the marginal imputation distribution conditional on the participant's observed outcomes (including observed post-SDCR ICE outcome assessments). A single deterministic imputation using the conditional mean from the conditional imputation distribution for each participant with missing outcomes will be used.

3. Analysis step

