Appendix 1 Type I Error Control Considerations for Reference-Based Conditional Mean Imputation Combined with the Jackknife for Inference

Introduction

In the GRADUATE trials, hypothetical and treatment policy strategies are applied to Non Study Drug or Condition Related (NSDCR) intercurrent events (ICEs) and Study Drug or Condition Related (SDCR) ICEs, respectively. That is, the clinical interest is in a scenario where SDCR ICEs but not NSDCR ICEs do occur. For estimating the treatment effect, data after NSDCR are assumed to be missing at random (MAR) whereas missing data after SDCR are imputed based on the placebo group in both treatment groups using the copy-increments-in-reference (CIR) imputation method, a specific type of reference-based imputation. We refer to Section 5.3.3 for further details.

The primary analysis of the GRADUATE trials is implemented using conditional mean imputation of missing data combined with the jackknife for inference. This methodology has been described and justified in Wolbers et al. (2022). In this appendix, we provide further details regarding type I error control of the method including additional simulations targeted to the setting of the GRADUATE trials.

Theoretical and published simulation evidence for type I error control

As demonstrated in Section 2.5 of Wolbers et al. (2022), the proposed conditional mean imputation methodology corresponds to a computationally efficient implementation of maximum likelihood multiple imputation. Estimators based on maximum likelihood imputation are asymptotically normal and unbiased if the imputation model and the associated missing data assumptions are correctly specified (Wang and Robins (1998), Robins and Wang [2000]). Moreover, standard error estimates based on resampling methods such as the jackknife or the bootstrap are consistent (Bartlett and Hughes (2020), von Hippel and Bartlett (2021), Wolbers et al. (2022)).

Therefore, large-sample (asymptotic) type I error control is guaranteed if the imputation model and the associated missing data assumptions are correctly specified. This is the case if the following conditions hold:

- All ICEs are correctly identified and classified as NSDCR or SDCR.
- Observed outcome data prior to an ICEs follow a multivariate normal mixed model for repeated measures (MMRM) with an unstructured covariance matrix.
- Missing outcome data prior to an ICE are missing at random (MAR).

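### The CDR-SB progressor analysis applies a cut-off to single conditional-mean imputations, which biases the progressor proportions, the threshold plot and the optional Cox model; the primary test is not affected

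*SAP*

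**What the plan says.** SAP Section 5.3.3 builds the primary estimator in four steps. In the imputation step: "A single deterministic imputation using the conditional mean from the conditional imputation distribution for each participant with missing outcomes will be used". Besides baseline CDR-SB and the visits, the imputation model includes "baseline ADAS-Cog 13 total score, baseline ADCS-ADL total score and the randomization stratification factors". After an NSDCR event, observed scores are deleted and "the missing data are assumed to be similar to those from the other participants in the same treatment group with no such missing data". After an event related to study drug or condition (SDCR), missing scores in the active arm follow placebo increments (CIR). SAP Table 3 anticipates four NSDCR event types: COVID-19 withdrawal, at least four dose-months missed because of COVID-19, death, and "Withdrawal from study treatment due to purely administrative reason".

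SAP Section 5.3.5.2 then sets the primary progression threshold at 2.5, estimates each arm's probability by the share of participants who reach x at some visit, and plots that share over a range of x. On the data: "The CDR-SB progression endpoint will be analyzed using the same conditional mean imputed dataset as for the primary estimator of the primary estimand". It may also fit a time-to-event model: "In addition, a Cox proportional hazard model to estimate the treatment effect on time to first CDR-SB progression". In that Cox paragraph: "Corresponding standard errors and confidence intervals will be calculated using the jackknife as previously described".

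Appendix 1 justifies the method by stating that "the proposed conditional mean imputation methodology corresponds to a computationally efficient implementation of maximum likelihood multiple imputation", and supports it with type I error simulations of the Week 116 mean comparison. Nothing there examines a thresholded endpoint.

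Clinically evident decline on the CDR is an exploratory endpoint in SAP Table 1. It is absent from Table 6, so Section 5.3.5.2 holds its only analysis.

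**The concern.** For an unobserved change with conditional mean m and conditional standard deviation s, the chance of having reached x at that visit is Φ((m − x)/s). The planned rule uses 1 if m ≥ x and 0 otherwise. A predicted change of 2.4 becomes certain non-progression and 2.6 certain progression. Averaging over participants does not cancel this. The equivalence to multiple imputation claimed in Appendix 1 holds for an estimator that is linear in the outcome, not for an indicator of crossing a cut-off. A jackknife estimates a standard error and leaves the bias in place.

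At x=2.5 the direction matters. Under the planning effect, the mean Week 116 changes of the two arms lie on either side of 2.5, so own-arm imputation after NSDCR events pushes the arms apart. What is at stake is a responder-type result that readers would use to judge clinical meaning.

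**Working it through.** **Plan's own figure.** Difference 0.30 × 2.5 = 0.75, SD 2.97, two-sided 5%, 90% power: 330 per arm. 660/(1 − 0.35) = 1015.4, so 1016, as stated in SAP Section 3.

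**Inputs (SAP Appendix 1 unless stated).** Mean change rises by 1 point to Week 52, then by 1.5 per year. SDCR odds rise 1.45-fold per point, with 80% drop-out afterwards. All data are missing after NSDCR events, and 5% of visits are missed otherwise. The scenarios are null, so I added the 30% slowing of SAP Section 3 at every visit. That is an assumption: the SAP states the effect for Week 104.

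The listed spreads (1.53 to 4.26) are labelled variances. Read so, Scenario 1 produces 16% SDCR events against 21% printed in Appendix 1 Table 3; read as SDs it produces 21%. I therefore lead with the SD reading and also give the printed one.

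**Hand check, Week 116 alone, participant at the mean baseline with no later score.** Placebo mean change: 1 + 1.5 × 64/52 = 2.85. Active: 0.7 × 2.85 = 1.99. Baseline correlation is 0.52, so s = 4.26 × √(1 − 0.52²) = 3.64 (SD reading) or √4.26 × √(1 − 0.52²) = 1.76 (variance reading).
- SD reading: Φ(0.35/3.64) = 54% placebo, Φ(−0.51/3.64) = 44% active.
- Variance reading: 58% and 39%.
- Planned rule: 100% and 0%.

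**Simulation.** Several hundred thousand participants per arm, known imputation parameters, conditioning on baseline CDR-SB and observed visits only. Placebo minus active at x=2.5, in points, complete data → planned rule (percentages from unrounded values):

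| Scenario | NSDCR, placebo/active | SD reading | Variance reading |
|---|---|---|---|
| 1 | 11/11% | 7.5 → 9.5 (+25 to 27%) | 16.4 → 20.9 (+27%) |
| 2 | 9/12% | 7.6 → 10.0 (+33%) | 16.1 → 20.7 (+29%) |
| 3 | 0/0% | 7.3 → 7.7 (+5%) | 15.7 → 16.7 (+6%) |
| 4 | 0/0% | 7.2 → 7.5 (+4%) | 15.5 → 16.1 (+4%) |

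In 400 trials of 508 per arm, with the imputation model refitted each time, the ratios were 1.26, 1.35, 1.05, 1.05 (SD) and 1.27, 1.29, 1.05, 1.04 (variance). The bias was 0.6, 0.8, 0.1, 0.1 standard errors (SD) and 1.3, 1.4, 0.2, 0.2 (variance).

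**Source.** Among NSDCR participants in Scenario 2 (SD reading), true progression is 69% placebo and 61% active; the planned rule gives 61% and 36%. Contributions: 0.09 × (61 − 69) = −0.7 and 0.12 × (36 − 61) = −3.0, which widens the difference by 2.3 of the total 10.0 − 7.6 = 2.4 points.

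**Cox model (unadjusted, Efron ties).** SD reading: hazard ratio 0.81 → 0.77 (Scenario 1) and 0.82 → 0.76 (Scenario 2). Variance reading: 0.64 → 0.57 and 0.65 → 0.58. Scenarios 3–4 move by about 0.02 or less.

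**Other thresholds.** At x=4 to 5 both arm proportions are 2–7 points too low. At x=5 the contrast ratios for Scenarios 1–4 are 0.92, 1.25, 0.98, 1.17 (SD) and 0.81, 0.94, 0.87, 0.96 (variance).

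**No drug effect.** At x=2.5 the spurious difference is below 1 point, and about 0 with equal event rates. With unequal rates it reaches about 1–2 points in favour of active drug at x=4.

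**Sensitivity, Scenarios 1–2 / 3–4.**
- Extra covariates explaining an assumed 10–30% of residual variance: 9–26% / 3–8%.
- Scores rounded to 0.5: 27–37% / 3–6%.
- Effect building up after titration: 28–39% / 2–4%.
- Spread rescaled to the design SD of 2.97: 25–49% / 4–8%.

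**Controls.** The Week 116 mean difference is preserved (Scenario 2, variance reading: −0.769 complete data, −0.773 conditional mean). Random draws from the same conditional distributions bring the x=2.5 contrast to within about 1% of the truth in every scenario.

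**The case against.** The strongest reply is that little hangs on this analysis. It is supplementary, it lies outside the testing hierarchy of SAP Section 5.1, and the Cox model is only a possibility. The 9–12% NSDCR share is an input to a type I error simulation, not a forecast. The main runs omit covariates that the SAP will use and that shrink the bias. All of this stands and limits the consequence. It does not make the estimator consistent: the covariates reduce the residual scatter without removing it, and no section adds random draws.

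Three stronger readings are tempting, and the documents do not support them.
- A reader might infer that the primary result or its type I error is compromised. The primary ANCOVA is linear in the outcome and its mean difference is unbiased in the same runs.
- A reader might infer that the rule always favours the drug. At higher x the direction varies with scenario and reading, and under the null the error at x=2.5 is small.
- A reader might take the range of a quarter to a third as what the trial will show. The sensitivities above span about 9–49% with NSDCR events.

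It would also go too far to say that the SAP plans jackknife errors for the proportions. That sentence sits in the Cox paragraph, and no standard error is stated for the proportions.

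**Conclusion.** The concern holds for the thresholded analyses only. As written, Section 5.3.5.2 gives biased progressor proportions and an unevenly distorted threshold plot, and would bias the Cox model if it is run. The x=2.5 contrast is overstated by roughly a quarter to a third with 9–12% NSDCR events and by about 3–7% without. This rests on the Appendix 1 set-up, a 30% effect at every visit, and imputation from baseline CDR-SB and observed visits alone. The relative size at x=2.5 is similar under both readings of the Appendix 1 spreads; the absolute size is not, and at x=5 even the direction can differ. Participants who finished at Week 104 before the extension are also imputed from their own arm and were not modelled. The change is worth making before unblinding because it is cheap and this is the endpoint's only analysis.

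**What to change.** Keep conditional-mean imputation for the ANCOVA.

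**Proportions and threshold plot.** For a participant with missing visits, replace the 0/1 value by the conditional probability of reaching x at any visit, under the same imputation model and the same MAR and CIR rules, computed numerically. CDR-SB moves in 0.5 steps, so apply x on that grid; with a continuous conditional distribution, use x − 0.25. State which standard error applies.

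**If random draws are used instead.** Use many draws and hold each participant's random numbers fixed across jackknife replicates, or bootstrap participants through the whole procedure. Do not redraw independently in each delete-one replicate: with 1016 participants this adds about 1015 times the Monte Carlo variance. In Scenario 2 (SD reading) a standard error of about 2.7 points would become about 7.9 with 25 draws, 3.8 with 200 and 2.9 with 1,000.

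**Cox model, if run.** Use draws rounded to the 0.5 grid, average the log hazard ratios, and pre-specify a bootstrap variance. This needs new text, because SAP Section 5.3.6 allows the bootstrap only after non-convergence.

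**Cost.** A few lines of SAP text, more computing, and some Monte Carlo noise where draws are used.
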